1.0 PROTOCOL SUMMARY AND/OR SCHEMA

Title: A Prospective Randomized Controlled Clinical Trial of Standard versus Goal-Directed Perioperative Fluid Management (GDT) for Patients Undergoing Liver Resection.

Null Hypothesis: Goal-directed fluid management does not impact the incidence of postoperative complications in patients undergoing liver resection.

Objectives: Determine the impact of goal-directed fluid therapy on the incidence of 30-day overall postoperative morbidity.

Patient Population: 270 Patients undergoing elective liver resection. 135 patients on each arm.

Design: Single-blinded, prospective randomized trial.

Agents: Standard volume replacement solutions (crystalloid and colloid) and vasoactive agents will be administered to reach the goals of resuscitation according to pre-established protocols.

Time to completion: 2 years

[figure not shown]
[figure not shown]

Chart 1. Flow of management through different phases of the protocol

MEMORIAL SLOAN-KETTERING CANCER CENTER IRB PROTOCOL

IRB#: 12-056 A(4)

2.0 OBJECTIVES AND SCIENTIFIC AIMS

Primary objective:

- Evaluate the impact of goal-directed fluid management on the incidence of overall postoperative morbidity in patients undergoing liver resection.

Secondary Objective:

- Assess the impact of GDT compared to standard fluid therapy on the total time patients experience low cardiac output perioperatively (i.e. intraoperative and in the first 24 postoperative hours).
- Assess the impact of GDT compared to standard fluid therapy on the total volume of fluid given intraoperatively and during the first 72 hrs postoperatively.
- Assess the impact of GDT compared to standard fluid therapy on the requirement for blood transfusion.
- Compare the total dose (mcg/kg) of vasoactive agents used in the first 24 hrs between the standard management and GDT groups.
- Measure the difference in end-organ perfusion markers between GDT and standard therapy for fluid management.
- Assess the impact of GDT compared to standard fluid therapy on net fluid balance for the total admission time.
- Assess the impact of GDT compared to standard fluid therapy on the systemic inflammatory response.

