4.0 OVERVIEW OF STUDY DESIGN/INTERVENTION

4.1 Design

Prospective single-blinded randomized trial. Eligible patients will be consented for the trial prior to surgery. However randomization will not occur until the operating room. After the liver has been resected, intraoperative randomization will be done by envelopes. Preoperative preparation and induction will be standard for all patients. In the OR all patients will have an arterial line placed preinduction and baseline hemodynamic data recorded from the Edwards EV1000 system. In the study, all intraoperative fluid therapy will be managed with the standard LCVP anesthetic technique for hepatic resection, and then at the completion of the resection all fluid therapy will be managed according to randomization arm (Goal-directed fluid therapy-**appendix 1** compared to standard fluid management- see detail below) for reconstruction and closure. In the postoperative phase, management will be standardized for both arms as outlines below.

During low central venous pressure (LCVP) anesthetic technique for partial hepatectomy, intraoperative fluid balance is divided in to two phases (as previously published)⁸:

- Prehepatic resection (the first phase), starts at anesthesia induction and ends at the completion of parenchymal transection and hemostasis. This phase takes advantage of fluid restriction and the vasodilatory effects of anesthetic drugs to provide LCVP anesthetic management. Fluid boluses and/or vasoactive drugs are administered at the discretion of the anesthesia provider to maintain systolic blood pressure > 90 mm Hg and urine output > 25 ml/hr while keeping the cvp <5 mmHg (currently, the vast majority of our patients do not require central line placement for the performance of liver resections. Low central venous pressure is assessed by the surgeon's direct assessment of the distention of the vena cava at the time of surgery). Maintenance fluid is 1cc/kg/hr.

Prior to proceeding to the second phase the intraoperative fluid management after the hepatic resection, patients will be randomized to either

Goal-directed fluid therapy (**see appendix 1**)

Standard fluid management (**see appendix 1**).

MEMORIAL SLOAN-KETTERING CANCER CENTER IRB PROTOCOL

IRB#: 12-056 A(4)

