10.0 EVALUATION DURING TREATMENT/INTERVENTION

- Preoperative data will be collected and recorded: date of birth, weight, height, complete metabolic panel, complete blood count, coagulation profile.
- Standard intraoperative monitoring will be carried out for all patients.
- GDT patients will also be monitored by CO, SV and SVV. These data will similarly be obtained and recorded for the patients in the standard management group but it will not be available for the treating practitioners.
- Further measures of end-tissue perfusion will be assessed with arterial lactate levels and DO₂ (oxygen delivery) at baseline (before incision), at completion of the resection phase (intraoperatively), upon arrival to PACU (0 hours postoperatively), and on the morning of POD #1.
- Assessment and recording of all intraoperative and postoperative complications; the latter being considered as those occurring on or after postoperative day 1 until postoperative day 30. Complications occurring intraoperatively and after surgery on

MEMORIAL SLOAN-KETTERING CANCER CENTER
IRB PROTOCOL

IRB#: 12-056 A(4)

the same day, are most likely technical in nature and will be considered perioperative complications in the analysis.

- Estimated operative blood loss.
- Cumulative volume used for resuscitation will be recorded (stratified by colloids and crystalloids)
- Total dose (mcg/kg) of pressors, inotropes or vasodilators used will be recorded and stratified by specific drugs.
- Volume and type of blood products transfused.
- Daily comprehensive metabolic panel, complete blood count (these will be recorded for seven days or until discharged if discharged earlier).
- Daily coagulation panel, discontinued by POD 3 if normal.
- Volume and type of fluid intake and output until POD 7 or patient tolerates oral intake of fluids > 400 ml/24 hrs
- Daily nasogastric tube drainage volume (if used) and length of NG drainage
- Daily weight until POD 7 or until patient tolerates oral intake of fluids > 400 ml/24 hrs.
- Day of tolerating oral intake of fluids > 400ml/24hrs
- Day of IV ≤ KVO
- Day of tolerating oral intake of solids
- Day of passage of flatus
- Day of foley removal.
- Day of passage of feces
- Day of discharge

Table 2. Details hemodynamic and laboratory values obtained at different stages. For laboratory values a 30 minute variation will be allowed to account for early or delayed sample collection in the PACU and/or surgical ward.

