14.0 BIOSTATISTICS

This is a randomized comparison of goal-directed compared to standard fluid management in patients undergoing liver resection. Primary endpoint is overall postoperative morbidity.

270 patients will be randomized 1:1 to the two arms. This sample size provides 80% power for detecting a 15% decrease in the proportion of overall postoperative complications (i.e regardless of grade of severity), assuming the standard arm will have a 30% complication rate (two-sided Type I error of 5%). It also allows for an interim analysis halfway through enrollment, using O'Brien-Fleming boundaries both for efficacy and futility. If $p \leq 0.005$ at the interim analysis enrollment will stop with the conclusion that goal-directed fluid management significantly decreases postoperative morbidity. If $p \geq 0.468$ at the interim analysis enrollment will stop with the conclusion that goal-directed fluid management does not significantly decrease postoperative morbidity. If $0.005 < p < 0.468$ then the trial will continue to full enrollment. With an approximate enrollment of 11 patients per month, accrual should be complete in 2 years.

Secondary endpoints will be compared between the two arms using the Wilcoxon rank-sum test, except for the categorical endpoints of blood transfusion and systemic inflammatory response, which will be compared using Fisher's exact test.

MEMORIAL SLOAN-KETTERING CANCER CENTER IRB PROTOCOL

IRB#: 12-056 A(4)

Since one of our main goals for this study is to establish what the individual amount of resuscitation is for each patient, tailored to their hemodynamic status, we decided to use their baseline value ± 2 standard variations as their homostatic stroke volume variation. An elevation above 2 standard deviations would be statistically unlikely to represent a normal variation of the measurement and will thus be considered a hemodincomically significant deviation from baseline.

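### Two secondary totals, and net fluid balance as worded in Section 2, start counting before patients are randomised, which adds noise and costs power but does not bias the comparison

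*Combined protocol and SAP*

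**What the plan says.** **Timing of allocation.** Section 4.1 states: "After the liver has been resected, intraoperative randomization will be done by envelopes". Section 15.2 repeats this. Before that point all patients have the same fluid-restricted low-CVP technique, from induction to the end of transection and haemostasis. During it, "Fluid boluses and/or vasoactive drugs are administered at the discretion of the anesthesia provider" to hold blood pressure and urine output (Section 4.1).

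**Windows of the secondary endpoints.**

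| Endpoint | Section 2.0 | Section 12.0 |
|---|---|---|
| Low-cardiac-output time | "total time patients experience low cardiac output perioperatively (i.e. intraoperative and in the first 24 postoperative hours" | no window |
| Fluid volume | "total volume of fluid given intraoperatively and during the first 72 hrs postoperatively" | perioperative |
| Net fluid balance | whole admission | 48 hours after surgery |
| Vasoactive dose | first 24 hours, no time zero | no window |
| Transfusion | no window | no window |

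**Perfusion markers.** Section 10.0 schedules lactate and oxygen delivery "at baseline (before incision), at completion of the resection phase (intraoperatively", then on arrival in the PACU and on the morning of POD 1.

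**Analysis.** Section 14.0: "Secondary endpoints will be compared between the two arms using the Wilcoxon rank-sum test". Fisher's exact test is used for transfusion and inflammatory response. No covariate is named.

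**The concern.** The secondary objectives ask what goal-directed therapy does to low-output time, fluid volume and net balance. Its effect can begin only when the envelope is opened. Whatever accrued earlier varies between patients for reasons unrelated to allocation, such as how long the resection took, and the planned test removes none of that variation. The signal is unchanged and the noise is larger.

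These endpoints would help to explain the primary result. If one of them shows no difference, a reader could not tell an absent effect from one masked by variation that arose before the arms existed.

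**Working it through.** **1. The plan's own figure.** The only power statement concerns the primary endpoint: "This sample size provides 80% power for detecting a 15% decrease in the proportion of overall postoperative complications", from 30% to 15%, two-sided 5%, 135 per arm. With mean proportion 0.225:

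n = [1.96 √(2 × 0.225 × 0.775) + 0.842 √(0.30 × 0.70 + 0.15 × 0.85)]² / 0.15² = 120.5, so 121 per arm (242 in total).

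With continuity correction: (120.5/4) × [1 + √(1 + 4/(120.5 × 0.15))]² = 133.5, so 134 per arm (268 in total). That reproduces 270 to within rounding. Fisher's exact power at 135 per arm is 81.0%. The timing of the secondary totals does not enter this calculation. No power is stated for any secondary endpoint.

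**2. Model for a whole-operation total.** Write T = P + Q, where P accrues before randomisation and Q after it. Treatment acts on Q only. Let k = SD(P)/SD(Q) and ρ = corr(P, Q). The expected difference between arms is the same for T as for Q. The standardised effect is multiplied by 1/√(1 + k² + 2ρk).

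**3. Illustration.** Assumed inputs, none from the documents: an effect of 0.40 SD on Q, and the k and ρ below. From the documents: 135 per arm. Power = Φ(d √(135/2) − 1.96), where d is 0.40 times the multiplier.

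| k | Multiplier, ρ = 0 | d | Power, ρ = 0 | Multiplier, ρ = 0.3 | Power, ρ = 0.3 |
|---|---|---|---|---|---|
| 0 (count from randomisation) | 1.00 | 0.400 | 91% | 1.00 | 91% |
| 0.25 | 0.97 | 0.388 | 89% | 0.91 | 85% |
| 0.5 | 0.89 | 0.358 | 84% | 0.80 | 75% |
| 1 | 0.71 | 0.283 | 64% | 0.62 | 53% |
| 2 | 0.45 | 0.179 | 31% | 0.40 | 26% |

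Example, k = 1 and ρ = 0: 0.283 × 8.216 = 2.324; 2.324 − 1.960 = 0.364; Φ(0.364) = 64%. A correlation below −k/2 would reverse the attenuation.

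**4. Check with the planned test.** In simulated rank-sum tests at 135 per arm, with an effect sized for 80% power by the normal approximation (0.341 SD), power was 78% counting from randomisation. Counting the whole operation gave 67%, 60% and 47% for variance ratios k² of 0.25, 0.5 and 1 (ρ = 0). With no treatment effect the rejection rate was 5.2% with P included (k = 1) and 5.1% without. The cost is power, not validity.

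**5. Which k is plausible for fluid volume?** Section 4.1 gives maintenance of 1 cc/kg/hr before resection, and standard-arm crystalloid of 6 cc/kg/hr times total operative time afterwards. Section 9.0 gives 1.2 ml/kg/hr after surgery. Assume a 4-hour operation with 3 hours before resection, and maintenance running for all 72 hours below its rate cap:

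- before randomisation: 3 × 1 = 3 ml/kg
- standard arm after resection: 6 × 4 = 24 ml/kg
- after surgery: 1.2 × 72 = 86.4 ml/kg

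The early share is 3/113.4, about 2.6%. If postoperative maintenance is left out it is 3/27, about 11%. Boluses and blood-loss replacement are excluded. A share of volume is not a share of variance, but this points to the upper rows of the table.

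**6. Low-output time.** The text gives neither a threshold for low output nor any phase durations, so k cannot be placed.

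**The case against.** **It is only imprecision.** The common phase precedes randomisation, so it is balanced in expectation, and the test already allows for chance imbalance. This stands. A reader might infer that the totals bias the comparison, inflate false positives or threaten the primary analysis. The documents do not support that, and step 4 shows the error rate is unchanged.

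**Only some endpoints are affected.** This also stands. Only low-output time and fluid volume name the intraoperative period, and net balance includes it only under Section 2.0. For vasoactive dose and transfusion the defect is a missing start time. One might infer that blood given before allocation is charged to an arm, but Section 4.1 states its red-cell rule only under the post-resection phase and documents no earlier transfusion. Lactate and oxygen delivery are time-point measures, so accumulation does not apply to them. Listing the end-of-resection sample in the series does not make it a between-arm outcome. Cytokine collection was discontinued.

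**The collection text already looks to the right phase.** Section 10.0 records the volume used for resuscitation, Section 9.0 equates resuscitation with the post-resection phase, and Section 4.1 ties pulse-wave recording to the intervention period. This suggests that post-resection capture is intended, but it does not redefine the windows in Section 2.0.

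**Low-output time need not be the worst case.** It is tempting to say that a phase designed to keep patients dry must dominate it. The documents do not say that this phase produces low output, and they have blood pressure and urine output maintained during it.

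**Whole-operation totals describe exposure.** They do, and they can stay for that purpose.

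**Conclusion.** As written, low-output time and fluid volume, and net balance in its Section 2.0 wording, count exposure that treatment cannot affect, and the planned test does not adjust for it. Vasoactive dose and transfusion may do the same because their start is undefined.

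The consequence is lower power and null results that are harder to interpret on these secondary endpoints. The size rests on an assumed 0.40 SD effect and an assumed SD ratio: 91% power becomes 89% at a ratio of 0.25, 64% at 1 and 31% at 2 with no correlation, and lower with positive correlation. The loss is probably small for fluid volume, given the protocol's own infusion rates, and unknown for low-output time. The point is modest, but worth acting on because the remedy is cheap.

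Part of the pre-resection course properly matters later. Replacement of blood loss, and the standard-arm volume tied to operative time, are given after allocation and remain in a total that starts at randomisation.

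**What to change.** In Sections 2.0, 12.0 and 14.0:

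- Start low-output time, fluid volume, net balance, vasoactive dose and transfusion at randomisation, and give each an explicit end.
- Report the pre-randomisation amounts as baseline and use them as a covariate where available, for example by rank-based ANCOVA.
- Reconcile the net-balance window, which is the whole admission in Section 2.0 and 48 hours after surgery in Section 12.0.
- Use the end-of-resection lactate and oxygen delivery as the pre-treatment baseline when comparing PACU-arrival and POD 1 values.
- Keep whole-operation totals as descriptive figures.

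**Cost.** A recorded randomisation time, and fluid and drug records split by phase. The phases are already defined, the monitor data are stored and downloadable, and the end-of-resection sample is already scheduled. The documents do not confirm that fluid and drug records are time-resolved, so this must be checked. The sample size does not change.

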- Replacement fluid for the patients in the GDT group will follow **algorithm A. (appendix 1)**
- Postoperatively, all patients will be kept in the PACU until the following morning. Management at this stage will be standardized and equal for both arms:
 - PACU standardized management (algorithm B):
 - Patients requiring continued mechanical ventilation will receive a tidal volume of 8 ml/kg body weight at a frequency of 6 to 12 breaths per minute to keep the end-tidal carbon dioxide between 35 to 40 mm Hg. Most patients will be extubated in the operating room and not require mechanical ventilation.
 - Maintenance IV crystalloid at 1.2 ml/kg/hr with a maximum rate of 130 ml/hr.
 - Strict Inputs and Outputs measured hourly in PACU.
 - Boluses of 250 ml of albumin solution (given over 20 minutes) will be administered for SBP < 90mmHg and/or urine output < 40ml/2hr.

MEMORIAL SLOAN-KETTERING CANCER CENTER IRB PROTOCOL

IRB#: 12-056 A(4)

- Medications mixed as per pharmacy protocol, to be included in daily input.
 - The use of vasoactive agents will be left to the discretion of the treating practitioner.
-
- When patients leave PACU, the arterial line will be removed upon transfer to the floor and fluid management will be as follows:
 - Maintenance IV crystalloid at 1.2 ml/kg/hr (maximum rate of 130 ml/hr) until taking > 400ml/24 hrs po, then d/c.
 - Urine output (UOP) to be maintained at 80ml/4 hours (20ml/hr averaged over 4 hour periods) with boluses of 500 ml crystalloid solution.
 - Lasix 10mg IV starting POD 2 for weight gain greater than 2kg pre operative weight if approved by treating practitioner.
 - If UOP is greater than 60ml/hr over 8 hours, IV rate may be decreased at the discretion of the treating practitioner.

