12.0 CRITERIA FOR THERAPEUTIC RESPONSE/OUTCOME ASSESSMENT

The null hypothesis is that GDT in patients undergoing liver resection does not alter the incidence of postoperative complications. A 15% decrease (from 30% to 15%) in the

MEMORIAL SLOAN-KETTERING CANCER CENTER IRB PROTOCOL

IRB#: 12-056 A(4)

incidence of 30-day complications will be considered clinically significant and will represent the primary outcome measure. The incidence of these will be assessed after each patient's postoperative visits.

Secondary outcomes include the impact of GDT on low cardiac output time, total volume of fluid used perioperatively, the requirement for blood transfusion, the total dose of vasoactive drugs, end-organ perfusion markers and the net fluid balance 48 hrs postoperatively.

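### Total fluid volume is compared without using preoperative weight, although most of the 72-hour total is prescribed per kilogram; adjusting for weight would narrow the interval at almost no cost.

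*Combined protocol and SAP*

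**What the plan says.** - **Endpoint.** Section 2 lists "total volume of fluid given intraoperatively and during the first 72 hrs postoperatively" as a secondary objective, and also net fluid balance. Neither is indexed to body size. The vasoactive objective in the same list is: "Compare the total dose (mcg/kg) of vasoactive agents used in the first 24 hrs".
- **Analysis.** Section 14: "Secondary endpoints will be compared between the two arms using the Wilcoxon rank-sum test". Only the categorical endpoints are excepted, and no covariate is named.
- **Fluid set per kilogram.** Section 4.1 gives maintenance of 1 cc/kg/hr before resection, continued after it in the GDT arm, and 6 cc/kg/hr times operative time in the standard arm. Section 9.0 gives, for the PACU, "Maintenance IV crystalloid at 1.2 ml/kg/hr with a maximum rate of 130 ml/hr", and the same rate and cap on the floor.
- **Fluid not set per kilogram.** Blood-loss replacement, SVV-guided albumin, and the 250 ml and 500 ml boluses (Sections 4.1 and 9.0).
- **Weight.** Section 10.0: "Preoperative data will be collected and recorded: date of birth, weight, height".

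**The concern.** If a large share of a patient's 72-hour volume is a rate multiplied by weight, heavy and light patients differ by litres for reasons unrelated to the strategy under test. An unadjusted comparison counts that spread as noise, although the variable that explains it is a baseline value already in the database. At stake is the width of the interval for the volume difference, which is the direct measure of what the two strategies deliver. A choice between mL and mL/kg would also be left open until after the data are seen.

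**Working it through.** **1. Numbers per arm.** The plan gives no power or SD for fluid volume. Its only sample-size figure concerns the primary endpoint: "This sample size provides 80% power for detecting a 15% decrease in the proportion of overall postoperative complications", from 30% to 15%.
- n = [1.96·√(2×0.225×0.775) + 0.8416·√(0.30×0.70 + 0.15×0.85)]² / 0.15² = (1.1575 + 0.4889)² / 0.0225 ≈ 121 per arm.
- With continuity correction: 134 per arm, 268 in all. The stated 270 (135 per arm) is reproduced closely.

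**2. One case by hand, intraoperative plus 72 hours.** From the plan: the rates above and 135 per arm. Assumed: weight 80 kg, SD 16 (CV 20%); operation 4 h, SD 1; postoperative maintenance 48 h, SD 14; blood loss lognormal, median 400 mL, log-SD 0.8; boluses half-normal, scale 800 mL, the same in both arms. The 6 cc/kg/hr formula is read as the whole standard-arm crystalloid rate. The cap of 130 ml/hr (which binds above 130/1.2 = 108 kg) and product terms are left out.

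| Source of variance (mL²) | GDT | Standard |
|---|---|---|
| Weight: (rate × hours) × 16 kg | (4 + 57.6) × 16 = 986; squared 971,407 | (24 + 57.6) × 16 = 1,306; squared 1,704,591 |
| Maintenance hours: 1.2 × 80 × 14 = 1,344 | 1,806,336 | 1,806,336 |
| Operative time: rate × 80 × 1 | 80² = 6,400 | 480² = 230,400 |
| Blood loss: 400²·e^0.64·(e^0.64 − 1) | about 272,000 | about 272,000 |
| Boluses: 800²·(1 − 2/π) | about 232,600 | about 232,600 |

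- Sum over both arms: weight 2,675,998; everything else about 4,858,700; total about 7,534,700.
- ANCOVA with one slope (the average, 71.6 mL/kg) leaves 2 × (10 × 16)² = 51,200 of the weight part.
- Variance ratio, unadjusted to adjusted: 7,534,700 / (4,858,700 + 51,200) = **1.53**.

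**3. Same case, intraoperative volume only.** The slopes are 4 and 24 mL/kg. The weight part is 64² + 384² = 151,552; everything else is 236,800 + 544,000 + 465,200 = 1,246,000. Ratio: 1,397,552 / (1,246,000 + 51,200) = **1.08**.

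**4. Simulated range.** With the cap applied, CV 20-25% and 36-48 h of maintenance, the ratio is about 1.4-2.2 for the 72-hour total and 1.1-1.2 for intraoperative volume. It moves most with the assumed spread of maintenance hours.

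**5. Second set of assumptions.** Weight SD 15-20 kg, operation 4 ± 1.2 h, about 55 h of maintenance, and net balance with urine output proportional to weight. Detectable difference = 2.8016·√(2/135)·SD, at 80% power. The variance ratio is the square of the ratio of the two detectable differences.

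| Endpoint | Variance due to weight | Detectable difference, unadjusted | Adjusted | Variance ratio |
|---|---|---|---|---|
| Intraoperative + 72 h | 41-54% | 591-682 mL | 442-477 mL | 1.70-2.17 |
| Intraoperative | 7-14% | 248-303 mL | 237-289 mL | 1.06-1.15 |
| Net balance | 10-14% | 610-652 mL | 578-609 mL | 1.11-1.15 |

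Under another assumption about urine output, also scaling with weight, the net-balance ratio is about 1.0.

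**6. Is the contrast detectable anyway?** The formulas differ by 5 cc/kg/hr: 5 × 80 × 4 = 1,600 mL. The unadjusted standardised difference for the 72-hour total is 0.81-0.93. At the low end, 0.81 × √(135/2) − 1.96 = 6.65 − 1.96 = 4.69, so power is essentially 100% without adjustment.

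**7. Division or adjustment?**

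| Standardised difference | mL | mL/kg | Adjusted for weight |
|---|---|---|---|
| Intraoperative + 72 h | 0.81-0.93 | 1.12-1.23 | 1.15-1.24 |
| Intraoperative | 1.81-2.21 | 1.70-2.17 | 1.90-2.30 |

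Division helps the 72-hour total but slightly harms intraoperative volume. Adjustment helps both.

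**The case against.** The case for leaving the plan alone is reasonable. Absolute volume is a legitimate endpoint and is what the objective asks about. Randomisation balances weight in expectation, and chance imbalance is already reflected in the standard error. Every magnitude rests on assumed SDs, and the ratios describe a difference in means, not the rank-sum statistic itself. All of that stands, and it limits the point to precision.

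Four stronger readings are tempting, and the documents support none of them:
- **That net balance suffers equally.** Net balance is intake minus output. If output also rises with weight, much of the weight effect cancels.
- **That mL should be replaced by mL/kg.** Blood-loss replacement, SVV-guided albumin and the fixed boluses are not per kilogram, and maintenance is capped. Dividing those parts by weight adds noise, notably in the intraoperative period, the phase where the arms are treated differently.
- **That weight imbalance biases the result.** This is the same precision loss described a second time.
- **That the eligibility limits show how much weight matters.** BMI 17 to 45 marks the extremes allowed, not the spread among enrolled patients.

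What the objection does not answer is why a recorded baseline variable that drives the prescribed rates should go unused.

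**Conclusion.** The point holds as a minor improvement to one secondary analysis. For the intraoperative-plus-72-hour total, leaving out weight inflates the variance of the arm difference about 1.4-2.2 times. The interval is then √1.4 = 1.18 to √2.2 = 1.48 times as wide as it need be. For intraoperative volume alone the factor is about 1.1-1.2, and for net balance there is little or no gain if urine output scales with weight. These sizes depend on the assumed weight spread and maintenance hours; the direction follows from the plan's per-kilogram rates.

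A reader might infer that the trial could miss the volume difference. The 1,600 mL built into the formulas would be detected with or without adjustment. That figure assumes equal bolus volumes in both arms, and the documents give no expected volume for SVV-guided albumin. Only if such albumin reduced the contrast to roughly 450-680 mL over 72 hours would adjustment bear on detection. The primary endpoint, its error rate and the sample size are not touched.

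**What to change.** In Section 14, keep total fluid volume in mL and state that the arms will be compared with adjustment for preoperative weight, by ANCOVA, or by rank ANCOVA if the distribution is skewed. Add mL/kg as a sensitivity analysis. The same adjustment may be applied to net fluid balance, with little gain expected; its time window differs between Section 2 (whole admission) and Section 12 (48 hours) and should be settled first.

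The cost is one extra covariate and a short amendment to the secondary analysis, made before fluid volumes are compared by arm. No new data or patients are needed.
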